### 4. STUDY DESIGN

This will be a single arm, controlled, blinded, multi-reader, multi-case (MRMC) study using a sequential design. The study will include 5-12 readers depending on qualifications and availability.

Imagio (IUS+OA) Training to be completed prior to any reads taking place. Read 1 is immediately followed by Read 2 within the same read session.

- Read 1 (Control): Mammogram (if available) + History + IUS (stills and videos provided), IUS Probability of Malignancy (POM) and BI-RADS scored and the data form locked.
- Read 2 (Test): Mammogram (if available) + History + IUS (stills and videos provided), and Imagio (IUS+OA) (stills and videos provided). An interim IUS POM and BI-RADS is recorded as well as a combined Imagio (IUS+OA) POM and BI-RADS Pre and Post SenoGram on separate data forms.

Read 1 reflects the information available to a radiologist when evaluating standard ultrasound images, taking under consideration the mass and patient history and assessing mammogram results as available. The History details to be provided are summarized under the Blinding section of the protocol. Read 1 (IUS reads) will serve as the control representing current clinical practice. Read 2 (IUS+OA) will be considered the test read and reflect a pre SenoGram IUS and Imagio (IUS+OA) POM and BI-RADS assessment in addition to a post SenoGram IUS and Imagio (IUS +OA) POM and BI-RADS assessment. Following the display of the SenoGram within the Post SenoGram data form, the IUS and OA feature scores are locked, and the reader is prompted to provide a Post SenoGram POM and BI-RADS. Once the Post SenoGram POM and BI-RADS are provided, the form is locked.

A total of 155 complete read sets from the original PIONEER Intention-to Diagnose (ITD) population will be randomly selected from within the PIONEER Study.

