1.1. Statistical and Analytical Plans

1.1.1. Definitions and General Considerations for Data Analysis

1. All calculations will be performed in a GCP-compliant environment using SAS statistical software, version 9.2 or later, StatXact, version 10 or later or OR-DBM MRMC (2.5) or later.
2. This Statistical Analysis Plan (SAP) is based on Clinical Trial Protocol Imagio Feasibility MRMC Study of Optoacoustic Images vs. Imagio Ultrasound to Guide Decision to Biopsy, September 24/November 1, 2018 – Version 3.0.
3. This study is a single arm, controlled, blinded, multi-reader, multi-case (MRMC) study using a sequential design.
4. This feasibility study will be registered at clinicaltrials.gov.
5. There will be up to 12 independent readers to evaluate images using standardized equipment at American College of Radiology (ACR).
6. All readers will read all images utilizing (IUS) and before (IUS+OA pre) and after the SenoGram (SG) prompt (IUS+OA post); prior to all image reads, all readers will have access to mammography images and a clinical history as collected in PIONEER.
7. A total of 155 complete read sets from the original PIONEER Intention-to-Diagnose (ITD) population will be randomly selected from within the PIONEER Study. Only once mass is to be selected per PIONEER subject.
 - Cohort 1 will consist of 75 benign and 45 malignant masses classified by CDU as BI-RADS 3 to 5 selected at random in proportion to the original distribution of Bi-RADS classifications among subjects in the PIONEER Study. To facilitate the alignment of the PIONEER Pivotal Study data with the Feasibility Study data, the mass image set sampling plan will select a proportion with and without mammograms for benign masses. [Note: mammograms were present for nearly all malignant masses.]
 - Cohort 2 will consist of 30 malignant masses with at least one false negative read from the PIONEER study to assess if the excess FN rate observed with OA in the PIONEER study can be reversed. The same proportional sampling strategy with respect to CDU Bi-RADS will be used. Cohort 3 will consist of five DCIS, lymphoma, or phyllodes masses; this will assess if these atypical cases do not introduce FNs or FPs. [Note: Due to the small size, Cohort 3 results will be listed only and not be summarized.]
8. Cohort data will not be combined across cohorts.

9. To assess intermediate performance an interim analysis is planned after each reader has completed at least 72 Cohort 1 masses.

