1.1.7. Effectiveness Analysis

There are no formal tests of hypotheses for this study. P-values that are generated will be regarded as descriptive statistics. IUS+OA pre-is OA before the SenoGram; IUS+OA post is the reader input OA after viewing the SenoGram. The following will be used to assess feasibility of a pivotal study.

Table 1: Effectiveness Analysis for Study Endpoints

Endpoints by Cohort	Analysis/Software
Cohort 1: Primary	

Gain in specificity IUS+OA post vs. IUS at fixed sensitivity (95-99%) interpolated from the ROC AUC curves. This analysis will be repeated for IUS+OA pre vs. IUS and IUS+OA post vs. IUS+OA pre.
 
A recommended pivotal study sample size will be determined using multiple sources, including OR-DBM MRMC sample size program.
 
Review of entire feasibility study report will be used to recommend efficacy endpoints for the pivotal study.
	
OR-DBM MRMC
 
Sample Size: OR-DBM-MRMC Power program, nQuery v7, SAS (PROC POWER), and/or PASS v15.05.

Cohort 1: Secondary	

Partial AUC: Difference (IUS+OA post vs. IUS) in partial ROC AUC curves for 95-99% sensitivity. This analysis will be repeated for IUS+OA pre vs. IUS and IUS+OA post vs. IUS+OA pre.
	
OR-DBM MRMC & methods as per McClish

Specificity and Sensitivity: Observed and model-adjusted specificity and sensitivity will be reported for IUS+OA post vs. IUS using a 2% POM cutoff.
 
These analyses will be repeated for
	
SAS PROC GEE and MIXED treating readers as independent observations and readers as correlated and then readers correlated and masses as independent.

IUS+OA pre vs IUS and IUS+OA post vs IUS+OA pre, and for POM cutoffs of 1%, 3%, 4%, and 5%.
	
Two-sided 95% confidence intervals for sensitivity and specificity will be computed for IUS, IUS+OA pre, the IUS+OA post, and the 3 pairwise differences.

Negative Likelihood Ratios (NLR) for IUS and IUS+OA post, NLR defined as $((1 - \text{observed sensitivity}) / \text{observed specificity})$
	
SAS: Univariate 95% CI for PLR and NLR with variances fit using the logarithmic transformation and the delta method, reference PIONEER Table 14.2.3.2.

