
b) Specificity at fixed sensitivity (98%) for SenoGram classification as in (a).
 
c) Partial AUC (over sensitivity range 95% to 99%, inclusive, using the McClish normalization) for SenoGram classification as in (a).
 
d) Partial AUC (over sensitivity range 95% to 99%, inclusive, using the McClish normalization) for SenoGram classification as in (a).
 
e) Sensitivity and specificity for SenoGram classification based on prediction intervals and the SenoGram threshold. The prediction will be considered inconclusive if the SenoGram threshold lies within the prediction interval; otherwise the interval prediction is treated the same as a probability prediction. As in (a), each cohort will be analyzed separately, with subgroup analysis for masses with and without mammogram BI-RADS data.
 
f) Specificity at fixed sensitivity (98%) for SenoGram classification using the prediction interval as in (d).
 
Partial AUC (over sensitivity range 95% to 99%, inclusive, using the McClish normalization) for SenoGram classification using the prediction interval as in (d).
	
PIONEER data.

Cohort 1: Exploratory
	

OA Feature Score Distributions:
 
 • Benign vs. malignant masses • Benign masses only – mammogram vs no mammogram 
POM Score Distributions:
	
Summary Statistics by reader. Average over readers and then summarize means for overall. Use Wilcoxon for test statistic.
 
Reference PIONEER T14.2.10.1 [t_14_02_1x_feat-10-_01]

 Benign vs. malignant masses Benign masses only – mammogram vs no mammogram 	Reference PIONEER Table 14.2.9.1 [t_14_02_09_pom-01]
Cohort 2: Secondary	
Observed and model-adjusted sensitivity	SAS: PROC GEE and MIXED
BI-RADS: Up and downgrades (defined above) for cancers only	
SAS: BI-RADS Grade Changes (Grouped BI-RADS), simple counts with two-sided 95% CI.
 
Cancers: Reference PIONEER Table 14.2.13.7 [t_14_02_13_birch2_07]
 
Note: change from 99% CI to 95% CI
 
Tables to be repeated for IUS x IUS+OA post, IUS vs IUS+OA pre and IUS+OA pre vs IUS+OA post

Cohort 3: Listings Only	

All Cohorts (Combined)
 
Summary statistics to describe the SenoGram usage [n(%)] by individual reader and overall. Summary statistics for the SenoGram effect on reader confidence.
	SAS: Proc Freq & Proc univariate

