1.1.7.1. Feasibility Analysis Methodology

Data Analyses

Hypotheses generating analyses will be based on independent readers for POM, BI-RADS and feature scores (IUS, IUS+OA pre, IUS+OA post) individually and overall. There are no formal hypothesis tests; p-values from all analyses are descriptive only. There are no adjustments for multiple testing. There will be no adjustment in p-values reported for the planned interim analysis after a minimum of 72 reads by each reader in Cohort 1. Truth (determination of malignant biopsy, benign biopsy, or TPB) will be taken from PIONEER.

The analyses below will be done for Cohort 1, repeated for malignant masses only for cohort 2. No summaries (listings only) will be done for the 5 masses in Cohort 3.

The specificity advantage of IUS+OA post vs IUS, IUS+OA pre vs IUS and IUS+OA post vs IUS+OA pre will be compared at fixed 98% sensitivity. The software package OR-DBM MRMC [Version 2.5 or later] will be used for this analysis of OA gain as interpolated from the ROC curves.

Specificity and sensitivity will be calculated by reader and overall for IUS, IUS+OA pre, IUS+OA post, and the 3 pairwise differences [PROC GENMOD, readers as independent,

repeated as masses as independent]. Specificity and sensitivity will be calculated (not model-adjusted) using the 2% POM cutoff for IUS+OA pre, IUS+OA post and IUS; and then for robustness analyses, for 1%, 3%, 4%, and 5% cutoffs.

Clinically relevant up and downgrades based on BI-RADs are defined as:

- Downgrades: IUS in BR 4a and IUS+OA post in BR 2-3 or IUS in BR 3 and IUS+OA post in BR 2
- Upgrades: IUS in BR 2 and IUS+OA post in BR 3-5 or IUS in BR 3 and IUS+OA post in BR 4-5.

These definitions likewise hold for differences for IUS vs IUS+OA pre and IUS+OA pre and IUS+OA post. These clinically relevant up and downgrades will be reported by reader and overall for benign and cancers separately. For benign masses, up and downgrades will be reported for masses with and without mammograms.

To assess the net effect of downgrades and upgrades, a net gain will be computed in SAS using contrast statements for the ANOVA to determine weight (W) of the malignant outcomes (TP and FN) to determine the value $(A-B+W(C-D))$ that achieves statistical significance, where A, B, C and D are defined as:

- A. Benign Masses correctly downgraded using IUS+OA post
- B. Benign Masses incorrectly upgraded using IUS+OA post
- C. Malignant masses correctly upgraded using IUS+OA post

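### The GEE run with readers as the independent units has only 5 to 12 clusters and no small-sample method; with the usual robust interval, its 95% CIs for the pairwise differences would cover about 85% to 91%.

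*SAP*

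**What the plan says.** SAP section 1.1.7.1 calculates specificity and sensitivity by reader and overall for IUS, IUS+OA pre and IUS+OA post, "and the 3 pairwise differences [PROC GENMOD, readers as independent", and then "repeated as masses as independent". SAP Table 1 (section 1.1.7, Cohort 1 secondary endpoints) describes the same analysis as "SAS PROC GEE and MIXED treating readers as independent observations and readers as correlated and then readers correlated and masses as independent". The row adds: "Two-sided 95% confidence intervals for sensitivity and specificity will be computed for IUS, IUS+OA pre, the IUS+OA post, and the 3 pairwise differences". For Cohort 2 sensitivity, Table 1 says only "SAS: PROC GEE and MIXED".

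On the number of readers, protocol section 4 says "The study will include 5-12 readers depending on qualifications and availability", and SAP section 1.1.1 also puts the maximum at 12.

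Neither document gives the GEE subject effect, a bias-corrected sandwich variance, a t or F reference, or denominator degrees of freedom for these models. Papers on degrees of freedom for multi-reader analysis appear in the reference lists. However, Table 1 assigns the OR-DBM MRMC software to the primary endpoint and the partial AUC, not to this row.

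**The concern.** The robust GEE interval relies on a large number of independent clusters. With readers as the clusters there are at most 12, each contributing 75 benign or 45 malignant Cohort 1 masses under three reads. More masses per reader do not help, because the sandwich variance is estimated from the spread between readers. Two things then make the interval too short: the uncorrected variance is biased downward, and 1.96 stands in for a larger t quantile. Both apply even if inference is to readers only with these masses held fixed, which is one of the analyses named in protocol section 9.8.

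The error favours optimistic conclusions. Protocol section 9.8 item 2 looks for superiority in specificity and non-inferiority in sensitivity in connection with 95% CIs for the OA-IUS differences, and a short interval makes both easier to claim. Protocol section 9.1 bases the move-forward decision on the primary and secondary endpoints together. It also uses Cohort 2 for separate reassurance that training reduced false negatives.

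**Working it through.** **Inputs from the documents.** Readers R = 5 to 12 (protocol section 4). Nominal two-sided level 95% (SAP Table 1). Masses per reader: 75 benign and 45 malignant (Cohort 1). Neither document gives variance components, so those used in the simulation are assumptions.

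**The plan's own figure.** The only stated figure is the 95% level. The question is whether 5 to 12 clusters deliver it.

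**Closed form.** Let d_k be reader k's paired difference in specificity (or sensitivity) between two modalities, and D the mean over R readers with equal numbers of masses.

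1. Uncorrected robust variance of D: sum of (d_k - D)² / R².
2. Unbiased variance of D: sum of (d_k - D)² / [R(R-1)]. The first is (R-1)/R times the second.
3. The robust interval with a normal quantile therefore has half-width c = 1.96 × sqrt((R-1)/R) unbiased standard errors.
4. If the d_k are normal, coverage is P(|t with R-1 df| < c). The t interval uses the 0.975 quantile of t on R-1 df in place of c.

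| R | c | coverage | t quantile | c / t quantile | t interval wider by |
|---|---|---|---|---|---|
| 5 | 1.753 | 84.6% | 2.776 | 0.63 | 58% |
| 8 | 1.833 | 89.1% | 2.365 | 0.78 | 29% |
| 10 | 1.859 | 90.4% | 2.262 | 0.82 | 22% |
| 12 | 1.877 | 91.3% | 2.201 | 0.85 | 17% |

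If the variance is rescaled by R/(R-1) but 1.96 is kept, coverage is P(|t with R-1 df| < 1.96): 87.8% at R = 5 and 92.4% at R = 12. No permitted number of readers reaches 95%.

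**Simulation with binary reads** (20,000 runs per setting, masses fixed, readers random). Assumed for the differences: specificity 0.40 with a gain of 0.10; sensitivity 0.97 with a loss of 0.01; on the logit scale, mass SD 1.5, reader SD 0.6 and reader-by-modality SD 0.2 or 0.5.

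| Difference | robust, normal: R = 5 | robust, normal: R = 12 | t interval, R = 5 to 12 |
|---|---|---|---|
| Specificity | 84% | 91% | 94.8-95.4% |
| Sensitivity | 86-87% | 91% | 95.0-95.6% |

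**Single sensitivities** (assumed 0.95 or 0.98, 45 masses, reader SD 0.3 or 0.8). On the probability scale the uncorrected interval covers 78-85% at R = 5 and 89-91% at R = 12. On the logit scale it covers 84-91% and 91-93%. A t interval on the probability scale gives only 89-95%, because the distribution is skewed near the ceiling.

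**Mancl-DeRouen alternative.** In the balanced case this correction multiplies the robust standard error by R/(R-1), whereas the unbiased standard error needs only sqrt(R/(R-1)). With t on R-1 df the interval is therefore wider than the reader-level t interval by sqrt(R/(R-1)): 12%, 7% and 4% at R = 5, 8 and 12. Coverage is 96.4%, 96.1% and 95.8%.

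**The case against.** The strongest objection is that the premise is inferred. The SAP names no subject effect, working correlation, variance estimator or quantile. Treating readers as independent could instead mean that different readers' reads of one mass are taken as uncorrelated, and protocol section 9.1 sets the unit of measurement at the reader-mass level. On that reading there are not 5 to 12 clusters and the figures above do not apply. This limits the claim to a conditional one. Reader as cluster is still the more natural reading, because section 1.1.7.1 sets this run against one with masses as independent.

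A second objection is that little depends on this interval. The SAP states no formal hypotheses and calls p-values descriptive. The move-forward criteria in protocol section 9.8 item 3 are illustrative, with no CI threshold. MIXED models and a mass-clustered run are reported alongside, and protocol section 9.8 adds an Obuchowski-Rockette analysis with readers and masses both random. All of this stands and lowers the importance. It does not make an interval labelled 95% accurate.

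A reader might infer more than the documents support:

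- That every interval in the row has 85-91% coverage. The range is for the differences; single sensitivities near the ceiling can fall outside it.
- That the judgement of inter-reader variability or the pivotal sample size is distorted. A GEE interval supplies no reader variance component, and the SAP bases sample size on the MRMC sample size program, possibly confirmed by other packages.
- That any disagreement between GEE and MIXED would be an artefact. The two may also treat masses and correlation differently, and protocol section 1.2 makes comparing several models an objective.

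**Conclusion.** The point holds conditionally. If the reader is the cluster and the usual robust variance and normal quantile are used, the nominal 95% intervals for the three differences in specificity and sensitivity cover about 85% with 5 readers and 91% with 12. They are 37% to 15% shorter than the t interval. The closed form assumes balanced data and normal reader-level differences with masses fixed; the binary-read simulation agrees under its assumed variance components.

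The effect is confined to one version of a secondary, descriptive analysis in Cohort 1 and the corresponding Cohort 2 sensitivity row. The mass-clustered run, with 75 benign or 45 malignant clusters in Cohort 1, and the primary OR-DBM analysis are untouched. It should be corrected because the results enter the move-forward judgement and the error runs towards claiming too much.

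**What to change.** In SAP Table 1 and section 1.1.7.1:

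- Name the reader as the cluster for this run.
- Replace its default interval for the three differences with the t interval on reader-level paired differences, on (readers - 1) df. With balanced data this is the robust variance multiplied by R/(R-1), with a t quantile.
- A Mancl-DeRouen variance with t on the same df is an acceptable, slightly conservative alternative (about 96% coverage). It is a different interval, so the SAP should name one of the two.
- For single sensitivities near the ceiling, work on the logit scale and state that coverage remains approximate.
- Apply the same rules to the Cohort 2 sensitivity row. Leave the mass-clustered run as it is.

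The cost is a sentence or two in the SAP and a few lines of SAS code, with no new data or design change. The intervals for the differences become about 58% wider at 5 readers and 17% wider at 12.

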### 1.2 Secondary Objectives

To evaluate the following overall and for individual readers for IUS versus Imagio (OA+IUS):

- the Imagio (IUS+OA) partial Receiver Operator Characteristic (ROC) Area under the Curve (AUC) for 95-99% vs IUS for 95-99% sensitivity
- the sensitivity and specificity for Imagio (IUS+OA) versus IUS according to multiple models for readers and masses used for assessing sources of variation
- the Negative Likelihood Ratio (NLR) for IUS versus Imagio (IUS+OA).
- the Imagio (IUS+OA) downgrades and upgrades relative to IUS, separately, for benign and malignant masses
- the net gain (new True Positives [TP] + new True Negatives [TN] – new False Positives [FP] – new False Negatives [FN]) estimate of Imagio (IUS+OA) versus IUS combining benign and malignant masses
- the usage and performance of the SenoGram model for the purposes of determining whether it will be adjusted prior to starting the pivotal study

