## 2.2 Secondary Endpoints

To evaluate the following overall and for individual readers for:

1. the partial ROC AUC corresponding to 95-99% sensitivity with specificities extrapolated from the respective Imagio and IUS ROC curves as applicable.
  - the observed and model-adjusted specificity and sensitivity
  - the Negative Likelihood Ratio (NLR) defined as  $((1-\text{sensitivity})/\text{specificity})$
  - the upgrade and downgrade metrics:
    - the percent correct of downgrades for benign masses from IUS BI-RADS 4a to Imagio (IUS+OA) BI-RADS 2-3, and from IUS BI-RADS 3 to Imagio (IUS+OA) BI-RADS 2
    - the percent incorrect of upgrades for benign masses from IUS BI-RADS 2-3 to Imagio (IUS+OA) BI-RADS 4-5 and from IUS BI-RADS 2 to Imagio (IUS+OA) BI-RADS 3-4-5
    - the percent of incorrect downgrades for malignant masses from IUS BI-RADS 4-5 to Imagio (IUS+OA) BI-RADS 2-3; and
    - the percent of correct upgrades for malignant masses from IUS BI-RADS 2-3 to Imagio (IUS+OA) BI-RADS 4-5.
2. the Cumulative effect of downgrades and upgrades for combined benign masses and malignant masses.
3. the SenoGram usage:
  - Utilization percent reported by the readers
  - Sensitivity and specificity discordance with Imagio (IUS+OA) Downgrades and upgrades versus Imagio (IUS+OA) and IUS, separately for benign and malignant masses
  - POM paired differences versus Imagio (IUS+OA) and IUS, separately for benign and malignant masses.
4. the SenoGram performance:
  - Sensitivity and specificity compared to sensitivity and specificity estimated from cross-validation and hold-out validation.
  - Partial AUC for individual users and overall corresponding to 95-99% sensitivity
  - Separate assessment of Senogram performance with and without mammographic data input.

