
BI-RADS (BR): Downgrade (IUS+OA post) defined as:
 
 • IUS in BR 4a and IUS+OA post in BR 2-3 or • IUS in BR 3 and IUS+OA post in BR 2 
BI-RADS: Upgrade defined as:
 
 • IUS in BR 2 and IUS+OA post in BR 3-5 or • IUS in BR 3 and IUS+OA post in BR 4-5 
Tables will be repeated for IUS x IUS+OA post, IUS vs IUS+OA pre and IUS+OA pre vs IUS+OA post.
	
SAS: BI-RADS Grade Changes (Grouped BI-RADS), simple counts with 95% CI.
 
Benign+TPB: Reference PIONEER Table 14.2.13.4 [t_14_02_13_birch1_04]
 
Cancers: Reference PIONEER Table 14.2.13.7 [t_14_02_13_birch2_07]
 
Note: change from 99% CI to 95% CI

Net grade change – All masses – weight (W) that results in a significant OA+IUS vs IUS reflecting the FP advantage minus the weighted FN disadvantage.
	
SAS: PROC GENMOD and MIXED linear models will contrast difference in FN and FP to demonstrate clinical benefit.
 
Tables to be repeated for IUS x IUS+OA post, IUS vs IUS+OA pre and IUS+OA pre vs IUS+OA post

SenoGram performance using the following metrics from the study endpoints:
 
a) Sensitivity and specificity for SenoGram classification based on predicted probability and the SenoGram threshold, with separate analysis for each study cohort and with subgroup analysis for masses with and without mammogram BI-RADS data.
	
For each metric, a summary table for each reader (where appropriate) and for all readers to contain the following:
 
 • Measured value using Reader-01 feature data. • Estimated value from SenoGram cross-validation with PIONEER feature data. • Estimated value from SenoGram predictions for cohort masses with

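### Net gain is defined as a change in true and false calls but computed from grade changes that do not match them, for benign and malignant masses alike

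*SAP*

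**What the plan says.** The documents describe net gain in two ways.

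*As a change in correct and incorrect calls.* Protocol 1.2 starts the sum with new true positives and continues: plus "new True Negatives [TN] – new False Positives [FP] – new False Negatives [FN]) estimate of Imagio (IUS+OA) versus IUS combining benign and malignant masses". The net grade change row of SAP Table 1 (section 1.1.7) describes the quantity as "reflecting the FP advantage minus the weighted FN disadvantage", and says the models "will contrast difference in FN and FP to demonstrate clinical benefit". Both documents attach the weight W to the malignant outcomes, which they label TP and FN.

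*As grade changes.* Protocol 2.2, item 2, lists the endpoint as "the Cumulative effect of downgrades and upgrades for combined benign masses and malignant masses". SAP 1.1.7.1 computes A−B+W(C−D), with these benign terms:

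- "A. Benign Masses correctly downgraded using IUS+OA post"
- "B. Benign Masses incorrectly upgraded using IUS+OA post"

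C and D are the malignant masses correctly upgraded and incorrectly downgraded. Just before this, the same section defines the moves that count. The first is "Downgrades: IUS in BR 4a and IUS+OA post in BR 2-3 or IUS in BR 3 and IUS+OA post in BR 2". Upgrades are 2 to 3-5, or 3 to 4-5. These changes are to be reported for benign masses and cancers separately, and no other definition is given for the cancers or for net gain. Protocol Table 4 labels the four terms only as masses picked up or lost.

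**The concern.** If A to D follow the SAP's grade-change definitions, the formula does not deliver the quantity that Protocol 1.2 names. Two kinds of move go wrong. Changes between BI-RADS 3 and 2 stay on the negative side of the diagnostic line, yet they are scored as gains or losses. Changes from 4b, 4c or 5 down to 2-3 cross the line, yet they are not scored at all, while the reverse moves from 2-3 up to 4-5 are scored in full.

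Net gain is a secondary endpoint intended to show clinical benefit. Protocol 9.1 bases the move-forward decision on the primary and secondary endpoints taken together, and SAP Table 1 uses the whole report to recommend pivotal endpoints. A net gain that partly reflects relabelling within the negative categories, or that ignores cleared high-suspicion masses, would inform those decisions under the wrong description. The same error passes into the search for W.

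**Working it through.** The documents give no numerical net gain, so there is no figure to reproduce. The check compares two scoring rules.

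**Inputs**

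- Categories: BI-RADS 2, 3, 4a, 4b, 4c, 5, giving 6 × 6 = 36 pairs of IUS and IUS+OA category.
- SAP rule (1.1.7.1): a downgrade is 4a→2-3 or 3→2; an upgrade is 2→3-5 or 3→4-5.
- Protocol 1.2 rule: new TN − new FP for benign masses, new TP − new FN for malignant masses.
- Positive line (an inference): 2-3 negative, 4a-5 positive. Three places support it. The SAP uses a 2% POM cutoff for sensitivity and specificity. Protocol 7.4 expands the scale for BI-RADS 3 while Protocol 9.8 item 5 expands 0-2%, which together put the upper end of BI-RADS 3 at 2%. The malignant rows of Protocol Table 1 count only moves between 2-3 and 4-5.

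**Pairs scored differently** (gain = +1, loss = −1)

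| Move | Benign: SAP / Protocol 1.2 | Malignant: SAP / Protocol 1.2 |
|---|---|---|
| 3→2 | +1 / 0 | −1 / 0 |
| 2→3 | −1 / 0 | +1 / 0 |
| 4b, 4c or 5 → 2 or 3 (six pairs) | 0 / +1 | 0 / −1 |

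That is 1 + 1 + 6 = 8 of 36 for each truth status; the other 28 agree. Writing n for the number of moves:

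- Benign error: (A−B) − (new TN − new FP) = n(3→2) − n(2→3) − n(4b-5→2-3).
- Malignant error, before weighting by W: (C−D) − (new TP − new FN) = n(2→3) − n(3→2) + n(4b-5→2-3).

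**Illustrations for one reader on benign masses (assumed counts)**

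| Moves | A−B | New TN − new FP |
|---|---|---|
| ten 3→2 | 10 − 0 = +10 | 0 |
| ten 3→2 and five 3→4a | 10 − 5 = +5 | 0 − 5 = −5 |
| five 4b→3 | 0 | +5 |
| ten 2→3 and five 4b→3 | 0 − 10 = −10 | +5 |

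The sign can be wrong in either direction. As a rough gauge, six 3→2 moves among the 75 benign masses of Cohort 1, with none opposing, give an exact two-sided sign-test p of 2 × 0.5⁶ = 0.031 with no change in false positives.

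**Malignant side.** Five malignant 4b→3 moves give C−D = 0, although they are five new false negatives. Protocol Tables 1 and 3 do count them: their malignant downgrades start from BI-RADS 4 or 5, and their malignant upgrades must reach 4-5. The protocol's malignant rows therefore agree with new TP − new FN; the SAP's definitions do not.

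**Why repairing A and B alone fails.** Take five benign and five malignant 4b→3 moves with W = 1. Protocol 1.2 gives 5 − 5 = 0. With only A and B redefined, the result is 5 + 0 = +5, in favour of OA.

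**The case against.** The strongest reply is that this is a grade-change endpoint by design. Protocol 2.2 and Protocol 9.8 item 2 describe it through downgrades and upgrades, the SAP row is called a net grade change, and Protocol Table 1 lists benign 3→2 as clinically significant. On that view the TP/TN/FP/FN wording is the loose text. This stands as far as showing that the documents conflict; it does not remove the conflict, because Protocol 1.2 and SAP Table 1 are explicit about false positives and false negatives.

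The SAP does not expressly tie A to D to its grade-change definitions, and no sentence places the positive line at BI-RADS 3/4a. Both are inferences, though well supported. At the SAP's 1% robustness cutoff, some 3→2 moves could change test status.

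Other analyses also limit the harm. SAP Table 1 reports the specificity difference at the 2% cutoff, and Protocol Table 2 lists 4a→3, 4a→2 and 3→2 in separate rows, so a benefit made only of relabelling would be visible.

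A reader might infer more: that the formula is tilted toward OA, or that it decides whether the pivotal study proceeds. The documents support neither. The error can take either sign. Net gain is not among the illustrative criteria in Protocol 9.8 item 3, p-values are descriptive, and no hypothesis is formally tested.

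**Conclusion.** The plan leaves net gain with two descriptions that do not agree. On the natural reading of SAP 1.1.7.1, the formula misscores 8 of 36 category pairs for benign masses and 8 of 36 for malignant masses relative to Protocol 1.2. The size of the resulting error depends on how often readers make those moves, which the documents do not give; the counts above are assumptions. For benign masses the error can run in either direction. For malignant masses the omission of 4b-5→2-3 always favours OA, while the moves between 2 and 3 can go either way. The conclusion rests on two inferences: that A to D use the SAP's only upgrade and downgrade definitions, and that the positive line lies between BI-RADS 3 and 4a. It should be corrected, but it is a secondary descriptive endpoint and does not affect the primary analysis.

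**What to change.** For the net-gain endpoint only, define all four terms by crossing one pre-specified positive line between BI-RADS 3 and 4a. State it as a single rule, not as a choice between BI-RADS and POM:

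- A: benign, positive on IUS and negative on IUS+OA
- B: benign, negative on IUS and positive on IUS+OA
- C: malignant, negative on IUS and positive on IUS+OA
- D: malignant, positive on IUS and negative on IUS+OA

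With that line, A−B equals new TN − new FP and C−D equals new TP − new FN for all 36 pairs. Apply the same rule to all three pairwise comparisons (post versus IUS, pre versus IUS, post versus pre). Keep moves between BI-RADS 3 and 2 in the descriptive upgrade and downgrade tables. Align the wording of Protocol 1.2, 2.2 and Table 4 with SAP Table 1 and 1.1.7.1 before results are seen.

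The cost is SAP wording and a recoded variable from data already collected. The reported net gain may become less favourable. With no missing reads, A−B will equal the number of benign reads times the specificity difference at the same line, so the benign half will largely repeat a result reported elsewhere.
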